4.4 Study Drug Dosing and Dose Modification

4.4.1 Dosing

Dosing calculations should be based on the body weight assessed at Cycle 1 Day 1 prior to the first dose of study drug administration. It is not necessary to recalculate subsequent doses if the patient's weight is within 10% of the weight used to calculate the previous dose. All doses should be rounded to the nearest milligram.

Patients should be carefully monitored for infusion reactions during study drug administration. If an acute infusion reaction is noted, patients should be managed according to the guidelines in Section 4.8 and Section 4.9. Patients must remain near the vicinity of a hospital with rapid access to an intensive care unit setting during the initial 48 hour period after treatment for the first two treatment cycles.

All vials are for single use only. Further instructions on study drug preparation and administration are provided in the Pharmacy Manual.

Please refer to the study schema for dosing as follows:

- Phase 1 Dose Escalation (Dosing on Day 1 of each 14-day cycle):
 - Cohort 1: Cabiralizumab 4 mg/kg + APX005M 0.03 mg/kg
 - Cohort 2: Nivolumab 240 mg + Cabiralizumab 4 mg/kg + APX005M 0.03 mg/kg
 - Cohort 3: Cabiralizumab 4 mg/kg + APX005M 0.1 mg/kg

- Cohort 4: Nivolumab 240 mg + Cabiralizumab 4 mg/kg + APX005M 0.1 mg/kg
- Cohort 5: Cabiralizumab 4 mg/kg + APX005M 0.3 mg/kg
- Cohort 6: Nivolumab 240 mg + Cabiralizumab 4 mg/kg + APX005M 0.3 mg/kg
- Phase 1b (Dosing on Day 1 of each 14-day cycle):
 - ALL patients: Nivolumab 240 mg + Cabiralizumab 4 mg/kg + APX005M at the RP2D

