6. Any Grade ≥ 3 AST/ALT elevation combined with total bilirubin $>2x$ ULN (for patients with Gilbert's syndrome, use bilirubin $\geq 2X$ baseline) or INR > 1.5 not on warfarin
7. Failure to recover from a treatment-related AE to baseline or \leq Grade 1 within 12 weeks of last dose of investigational product (except Grade 2 alopecia and Grade 2 fatigue)
8. Any death not clearly due to the underlying malignancy or extraneous causes (e.g. car accident)
9. Recurrence of Grade 4 rash, or other Grade 3 immune-related AE (irAE), or Grade 4 infusion-related AE. Recurrent grade 3 infusion reactions should be discussed with the study PI.
10. Any toxicity requiring dose reduction of APX005M or permanent discontinuation of any of the study drugs.

irAE is defined as a clinically significant AE that is associated with study drug exposure, with the exception of AEs related to cytokine release, attributable to APX005M, and is consistent with an immune-mediated mechanism.

Certain toxicities, even if already resolved, will make it unacceptable to advance to subsequent cohorts as planned, including but not limited to:

- Grade 4 myocarditis; Grade 3 myocarditis will need to be discussed with the study PI
- Grade 3 neurotoxicity with the exception of peripheral neuropathy
- Grade 4 pneumonitis
- Bone marrow aplasia

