4.4.1.3 APX005M Dosing

All patients in all cohorts of the trial will receive APX005M as follows:

- Phase 1:
 - Cohorts 1 and 2: APX005M 0.03 mg/kg
 - Cohorts 3 and 4: APX005M 0.1 mg/kg
 - Cohorts 5 and 6: APX005M 0.3 mg/kg
- Phase 1b:
 - At the determined RP2D

APX005M is administered on Day 1 of each 14-day treatment cycle approximately 30 minutes following cabiralizumab using a 60 minute IV infusion. A window between -5 minutes and +10 minutes is permitted (i.e., infusion time is 55 minutes to 70 minutes).

Premedication should have already been administered 30 minutes prior to first dose of study drug, as described in Section 4.4.1.1. When the time between premedication and scheduled APX005M administration exceeds 4 hours, patients may receive an additional course of premedication prior to APX005M administration.

The APX005M infusion can be interrupted in the case of a grade 1-2 infusion reaction (see Section 4.8 and Section 4.9). Once symptoms resolve, infusion should be restarted at 50% of the initial infusion rate (e.g., from 50 mL/hr to 25 mL/hr). For a grade 3 infusion reaction, APX005M should be held and the investigator should dose reduce with the next cycle. Grade 4 infusion

reactions require discontinuation of APX005M.

The Pharmacy Manual contains specific instructions for the preparation of the APX005M infusion and administration of infusion solution.

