4.9 Criteria for Holding, Discontinuing, or Modifying Study Drug

Management of suspected adverse drug reactions may require temporary treatment hold (until re-treatment criteria are met), reducing the dose of APX005M, or discontinuation of some or all investigational products as per Table 5. If a subject experiences several toxicities, the recommended dose modification should be based on the highest grade toxicity.

Up to two dose reductions are permitted for APX005M. There are no dose reductions for cabiralizumab or nivolumab.

Table 5: Criteria for Holding, Discontinuing, or Modifying Study Drug

	Toxicity	Grade	APX005M	Cabiralizumab	Nivolumab
Gastrointestinal AEs	Diarrhea/colitis	2-3	1 st occurrence: Hold	Hold	Hold
			2 nd occurrence: dose reduction [¥]	If not improving in 28 days with oral steroids: Discontinue	If not improving in 28 days with oral steroids: Discontinue
	Vomiting	4	Discontinue	Discontinue	Discontinue
Endocrine AEs	Hypophysitis/ Endocrinopathies	2-4	Hold only if clinically unstable	Hold only if clinically unstable	Hold only if clinically unstable

	Toxicity	Grade	APX005M	Cabirizumab	Nivolumab
	Hyperthyroidism	2-4	Hold only if clinically unstable	Hold only if clinically unstable	Hold only if clinically unstable
Hepatic AEs	Increased AST/ALT	3 (> 5 to ≤ 12x ULN) and bilirubin <2x ULN	Continue	Continue	Continue
		3 (> 12x ULN) for >14 days and not decreasing on steroids and bilirubin <2x ULN	Hold	Hold	Hold
		2-3 and total bilirubin >2x ULN or 3x baseline for patients with Gilbert's syndrome and no cholestasis or INR >1.5 not on warfarin	Discontinue	Discontinue	Discontinue
		4	Discontinue	Discontinue	Discontinue
Increased bilirubin	Increased bilirubin	2	Hold	Hold	Hold
		3	Hold If >48 hours with no cholestasis or > 5 days with cholestasis: Discontinue	If >48 hours with no cholestasis or > 5 days with cholestasis: Discontinue	If >48 hours with no cholestasis or > 5 days with cholestasis: Discontinue
		4	Discontinue	Discontinue	Discontinue

	Toxicity	Grade	APX005M	Cabiralizumab	Nivolumab
Skin AEs	Rash or other skin toxicity	3	Hold If not improving in 28 days: Discontinue	Hold If not improving in 28 days: Discontinue	Hold If not improving in 28 days: Discontinue
		4	Hold If not improving in 28 days: Discontinue	Hold If not improving in 28 days: Discontinue	Discontinue
Neurological AEs	Neurological Toxicity	2	Continue	Continue	Hold
		3	Hold	Hold	1 st occurrence: Hold 2 nd occurrence: Discontinue
		4	Hold	Hold	Discontinue

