4.10 Dose Reduction

Dose reduction for nivolumab and cabiralizumab are not permitted. Dose reduction for APX005M is permitted as below and as per Section 4.8 and Section 4.9.

¥APX005M Dose Reductions

Dose Level (mg/kg)	DL1 (0.03)	DL2 (0.1)	DL3 (0.3)
First Dose Reduction	0.01	0.06	0.2
Second Dose Reduction	Not applicable	0.03	0.1

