4.14 Treatment Compliance

Study drug will be administered by qualified trained site personnel in the clinical facility. The Investigator or their designated study personnel will maintain a log (Drug Accountability Log) of all study drugs received dispensed and destroyed. The Investigator and the study personnel will ensure that each patient receives the calculated dose of the study drug based on body weight.

Drug supplies will be inventoried and accounted for throughout the study. The Drug Accountability Log will be reviewed by the PI during site visits and at the completion of the study. Any discrepancy should be brought to the attention of the Sponsor. Records of study medication administration (date, start and stop time, and dose administered relative to time of preparation) will be recorded on the patient's CRF.

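### Whole-milligram rounding cannot deliver the tabulated APX005M reduction from 0.03 mg/kg: it gives 0 mg below 50 kg and a 50% cut instead of 66.7% from 50 to 83.3 kg

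*Combined protocol and SAP*

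**What the plan says.** Section 4.4.1 (Dosing) bases doses on Cycle 1 Day 1 body weight and adds: "All doses should be rounded to the nearest milligram". The sentence covers every study drug. The protocol sets no minimum APX005M dose, and the eligibility criteria in Sections 3.2.2 and 3.2.3 set no minimum body weight.

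Section 4.9 says: "Up to two dose reductions are permitted for APX005M". Section 4.10 then says: "Dose reduction for APX005M is permitted as below and as per Section 4.8 and Section 4.9". Its table gives these steps:

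| Starting level (mg/kg) | First reduction | Second reduction |
|---|---|---|
| 0.03 | 0.01 | none |
| 0.1 | 0.06 | 0.03 |
| 0.3 | 0.2 | 0.1 |

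So 0.01 mg/kg is the only reduction open to a patient who starts at 0.03 mg/kg, as in Cohorts 1 and 2. A reduction can be required. Section 4.4.1.3 says: "For a grade 3 infusion reaction, APX005M should be held and the investigator should dose reduce with the next cycle".

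Preparation details lie outside the protocol: "The Pharmacy Manual contains specific instructions for the preparation of the APX005M infusion and administration of infusion solution". That manual is not among the documents.

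**The concern.** Rounding to a whole milligram is harmless for cabiralizumab at 4 mg/kg, where doses run to hundreds of milligrams. It is coarse for APX005M. At 0.01 mg/kg an adult's exact dose is usually below 1 mg, and at 0.03 mg/kg it is about 1 to 4 mg. The rounding unit is then as large as the dose, or a large fraction of it.

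At the lowest dose level the plan therefore gives two instructions that cannot both be met for a light patient: give 0.01 mg/kg, and round to a whole milligram. Whoever prepares the dose must either omit APX005M or depart from the rounding rule. Section 4.6 allows a drug to be held while others continue, but that is a different action from the tabulated reduction. For heavier patients a reduction is delivered, but often not the one in the table. What is at stake is whether the nominal level and the delivered dose agree at the bottom of the dose range.

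**Working it through.** The plan states no figure of its own on this point, so there is nothing to reproduce. The check is direct arithmetic.

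**Inputs.** Rounding unit 1 mg (Section 4.4.1). Levels 0.03, 0.01 and 0.06 mg/kg (Sections 4.4.1.3 and 4.10). Vial strength 10 mg/mL (Section 4.2.3). Assumed, because the documents give no weights: body weight 40 to 150 kg in steps of 0.1 kg, with exact halves rounded up.

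**Formulas.** Delivered dose = level × weight, rounded. Error = delivered dose / exact dose − 1. Delivered cut = 1 − (rounded lower dose / rounded higher dose). Intended cut = 1 − lower level / higher level.

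**Step 1: 0.03 to 0.01 mg/kg.** Intended cut = 1 − 0.01/0.03 = 66.7%.

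| Weight (kg) | Start (mg) | Reduced (mg) | Delivered cut |
|---|---|---|---|
| 40 to 49.9 | 1 | 0 | 100% |
| 50 to 83.3 | 2 | 1 | 50% |
| 83.4 to 116.6 | 3 | 1 | 66.7% |
| 116.7 to 149.9 | 4 | 1 | 75% |

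Examples:
- At 45 kg, 1.35 mg rounds to 1 mg and 0.45 mg rounds to 0 mg.
- At 70 kg, 2.10 mg rounds to 2 mg and 0.70 mg rounds to 1 mg. The reduced dose is 1/70 = 0.0143 mg/kg instead of 0.01.

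The tie rule matters to the under-50 boundary only at exactly 50.0 kg, where rounding halves to the even number would give 2 mg to 0 mg.

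**Step 2: the 0.03 mg/kg dose itself.**
- At 49.9 kg: exact 1.497 mg, given 1 mg. Error = 1/1.497 − 1 = −33%, or 0.020 mg/kg.
- At 50 kg: exact 1.50 mg, given 2 mg. Error = 2/1.5 − 1 = +33%, or 0.040 mg/kg.
- The error exceeds 20% only from 41.7 kg (1/1.251 − 1 = −20.1%) to 55.5 kg (2/1.665 − 1 = +20.1%).

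**Step 3: 0.06 to 0.03 mg/kg, the second reduction from 0.1 mg/kg.** Intended cut 50%.
- 41.7 to 49.9 kg: 3 mg to 1 mg, a 66.7% cut.
- 50 to 58.3 kg: 3 mg to 2 mg, a 33.3% cut.
- At all other weights in the range the cut lies between these two values. It never reaches 0 mg.

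**Step 4: the same steps with APX005M rounded to 0.1 mg.**
- 0.03 to 0.01 mg/kg: cuts from 64.3% (45 kg, 1.4 to 0.5 mg) to 69.2% (44.9 kg, 1.3 to 0.4 mg).
- 0.06 to 0.03 mg/kg: cuts from 48% (41.7 kg, 2.5 to 1.3 mg) to 52% (41.6 kg, 2.5 to 1.2 mg).
- Largest rounding error: 11.1% at 0.01 mg/kg and 3.9% at 0.03 mg/kg. No dose is zero.

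**Step 5: can 0.1 mg be measured?** At 10 mg/mL, 0.1 mg is 0.01 mL. Doses of 0.4 to 1.5 mg at 0.01 mg/kg are 0.04 to 0.15 mL of undiluted drug. If the measuring error is 0.01 mL (assumed), that is 0.01/0.04 = 25% at the smallest dose, more than the 11.1% rounding error. After a tenfold dilution to 1 mg/mL (illustrative) the smallest volume is 0.4 mL and the same error is 0.01/0.4 = 2.5%.

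**Step 6: how many patients.** Cohorts 1 and 2 hold 3 or 6 patients each under 3+3, so 6 to 12 in all. The documents give neither the share under 50 kg nor the share reduced. Assuming 5% to 15% and 10% to 30%, the expected number with a zero dose is 6 × 0.05 × 0.10 = 0.03 to 12 × 0.15 × 0.30 = 0.54.

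**The case against.** The strongest reply is that a specific tabulated reduction should prevail over a general rounding sentence, that a 0 mg order would prompt a query, and that the Pharmacy Manual may already deal with sub-milligram doses. Any of these may well happen in practice, and the manual cannot be checked. None removes the conflict in the protocol: the rounding sentence covers all doses, and no section exempts APX005M or sets a floor. If the manual rounds more finely, it departs from the protocol and the sentence still needs correcting.

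The second reply is that little follows from the problem. That stands, and several stronger inferences should be set aside:

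- **A breach of Section 4.14.** That section says: "The Investigator and the study personnel will ensure that each patient receives the calculated dose of the study drug based on body weight". A reader might infer that a rounded or zero dose violates it. It need not, because the calculated dose can be the one that Section 4.4.1 yields after rounding.
- **A distorted DLT count.** Item 10 of the DLT definition already counts "Any toxicity requiring dose reduction of APX005M or permanent discontinuation of any of the study drugs". A toxicity in the first 28 days that calls for a reduction is a DLT whatever amount is given afterwards.
- **A PK effect.** Section 1.3.6.3.2 reports that exposures at 0.03 mg/kg or less were mostly below the limit of quantitation.
- **A hidden omission or a hazard.** Section 4.14 provides that "Records of study medication administration (date, start and stop time, and dose administered relative to time of preparation) will be recorded", so a zero dose would be visible. Omission after toxicity means less exposure. From 50 to 83.3 kg the patient still gets a real reduction, half the starting dose.
- **A large Phase 1b problem.** The zero-dose case would reach the expansion cohorts only if 0.03 mg/kg became the RP2D, and nothing in the documents points to that.

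Dose levels also stay distinct: delivered doses at 0.03 mg/kg run from about 0.02 to 0.04 mg/kg, well below 0.1.

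**Conclusion.** The point holds as a minor internal inconsistency. With whole-milligram rounding the protocol cannot deliver its only reduction from 0.03 mg/kg as tabulated, except from 83.4 to 116.6 kg, where the delivered cut matches. The departures that matter are the zero dose below 50 kg and the shortfall in the cut from 50 to 83.3 kg. The error in the 0.03 mg/kg dose and the uneven 0.06 to 0.03 mg/kg step come from the same rule and are smaller in consequence.

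The scope is mainly patients dosed at or reduced to 0.03 mg/kg or below. Under the assumed rates, fewer than one zero-dose patient would be expected in Cohorts 1 and 2. The weight bands rest only on the protocol's levels and on rounding exact halves up. The patient count rests on assumed weight and reduction rates, and the practical effect depends on a Pharmacy Manual that is not available.

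**What to change.** Amend Section 4.4.1 so that APX005M doses are rounded to the nearest 0.1 mg and other weight-based doses to the nearest milligram. Nivolumab needs no mention because it is a flat 240 mg.

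Pair this with a pre-dilution step in the Pharmacy Manual for APX005M doses of a few milligrams or less. Without it, measuring error on very small undiluted volumes could undo the gain at the lowest doses.

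The cost is one amended sentence, a pharmacy check of small-volume preparation, and one extra dilution step for low doses, with the added handling that this brings.

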4.4.1.1 Nivolumab Dosing

The following patients on the trial will receive nivolumab as follows:

- Phase 1:
 - Cohorts 1, 3, and 5: will NOT receive nivolumab
 - Cohorts 2, 4, and 6: nivolumab 240 mg IV
- Phase 1b:
 - All patients will receive nivolumab 240 mg IV as the first drug in sequence

Nivolumab will be dosed as a 30-minute IV infusion on Day 1 of each 14-day treatment cycle as above.

Routine premedication administered 30 minutes prior to nivolumab should include:

- H1 antagonist (e.g. Benadryl 25 mg PO)
- Oral or IV H2 antagonist (e.g., ranitidine 150–300 mg, cimetidine 300–800 mg, nizatidine 150–300 mg, and famotidine 20–40 mg)
- Oral nonsteroidal anti-inflammatory drug (may comprise ibuprofen 400 mg or equivalent)
- Acetaminophen 650 mg

If a grade 1-2 infusion reaction is observed during the proposed infusion rate of nivolumab 240 mg over 30 minutes, the infusion rate will be extended to 60 minutes. Nivolumab should be held for a grade 3 infusion reaction and retreatment should be discussed with study PI. Nivolumab should be discontinued for a grade 4 infusion reaction.

There will be no dose escalations or reductions of nivolumab allowed. Refer to the Pharmacy Manual for nivolumab preparation instructions.

4.4.1.2 Cabiralizumab Dosing

All patients in all cohorts of the trial will receive cabiralizumab.

Cabiralizumab will be administered as a fixed dose of 4 mg/kg given over 30 minutes by IV infusion. In phase 1 dose escalation cohorts 1, 3, and 5, cabiralizumab will be given first

followed by APX005M. In this case, premedications outlined in Section 4.4.1.1 should be given 30 minutes prior to cabiralizumab on Day 1 of each 14-day treatment cycle.

In phase 1 dose escalation Cohorts 2, 4, and 6, and in all patients on the phase 1b portion of the trial, cabiralizumab will be administered 30 minutes after the end of the nivolumab infusion, on Day 1 of each 14-day treatment cycle.

If any Grade 3 or higher infusion reaction is observed during the proposed infusion rate of cabiralizumab 4 mg/kg over 30 minutes, cabiralizumab should be discontinued permanently. For further management of infusion reactions, please see Section 4.8 and Section 4.9.

A research pharmacist (or other responsible personnel) will prepare the solution for administration. After calculating the number of vials, based on the patient's weight, the study drug product will be diluted with 0.9% Sodium Chloride Injection, USP. Prepared cabiralizumab should be administered within 6 hours after preparation (ambient temperature). The IV administration setup for cabiralizumab infusion must contain a 0.2 or 0.22 μ m in-line filter or a 0.2 or 0.22 μ m syringe filter. Cabiralizumab will be administered under medical supervision as a 30 minute (\pm 5 minutes) IV infusion via a peripheral vein or central venous catheter. No incompatibilities between cabiralizumab infusion and polyvinyl chloride (PVC), ethylene/propylene IV components, or glass bottles have been observed.

4.4.1.3 APX005M Dosing

All patients in all cohorts of the trial will receive APX005M as follows:

- Phase 1:
 - Cohorts 1 and 2: APX005M 0.03 mg/kg
 - Cohorts 3 and 4: APX005M 0.1 mg/kg
 - Cohorts 5 and 6: APX005M 0.3 mg/kg
- Phase 1b:
 - At the determined RP2D

APX005M is administered on Day 1 of each 14-day treatment cycle approximately 30 minutes following cabiralizumab using a 60 minute IV infusion. A window between -5 minutes and +10 minutes is permitted (i.e., infusion time is 55 minutes to 70 minutes).

Premedication should have already been administered 30 minutes prior to first dose of study drug, as described in Section 4.4.1.1. When the time between premedication and scheduled APX005M administration exceeds 4 hours, patients may receive an additional course of premedication prior to APX005M administration.

The APX005M infusion can be interrupted in the case of a grade 1-2 infusion reaction (see Section 4.8 and Section 4.9). Once symptoms resolve, infusion should be restarted at 50% of the initial infusion rate (e.g., from 50 mL/hr to 25 mL/hr). For a grade 3 infusion reaction, APX005M should be held and the investigator should dose reduce with the next cycle. Grade 4 infusion

reactions require discontinuation of APX005M.

The Pharmacy Manual contains specific instructions for the preparation of the APX005M infusion and administration of infusion solution.

4.5 Blinding/Unblinding

This is an open-label study and there will be no blinding or unblinding of patients during this study.

4.6 Dose Modifications, Delays or Discontinuation

Doses of study drugs may be interrupted, delayed, or discontinued depending on how the patient tolerates the treatment. Dose reductions for nivolumab and cabiralizumab are not permitted. Dose reduction for APX005M is permitted as per Section 4.8 and Section 4.9.

If there is an infusion reaction or other unforeseen delay that makes dosing of APX005M impractical on the same day as nivolumab and cabiralizumab, the patient may be infused with APX005M the following day at the discretion of the Investigator.

Administration of nivolumab, cabiralizumab and/or APX005M combination therapy should be skipped for the following reasons:

- The treating physician determines that the patient would benefit from a break in treatment due to non-life threatening grade 1-2 toxicities such as fatigue, arthralgias or edema.
- Any drug-related laboratory abnormalities would not require a dose delay unless clinically indicated or specified in the protocol or abnormal laboratory management guidelines (see Section 4.8 and Section 4.9). Please discuss with the PI as needed.
- For dose delays or modifications for all other AEs please refer to the AE management guidelines in Section 4.8 and Section 4.9.

If the causality of the AE requiring a dose delay is confirmed to be due to one of three study drugs, then the non-offending drug may be continued per protocol taking into account the safety and clinical benefit to the patient.

4.7 Criteria to Resume Treatment with APX005M, Cabiralizumab and Nivolumab

Patients may resume treatment with APX005M, cabiralizumab and/or nivolumab when the drug-related AE resolves as noted in Section 4.8 and Section 4.9.

A new treatment cycle should be initiated only if all toxicities are \leq Grade 1 except:

- Grade 2 neuropathy lasting shorter than 28 days (hold nivolumab only)
- Grade 2 alopecia
- Grade 2 rash or other skin toxicity
- Grade 2 hypophysitis/endocrinopathies
- Grade 2 fatigue
- Grade 2-3 neutropenia/lymphopenia
- CK increase up to 15x ULN

- AST/ALT \leq 12x ULN for \leq 7 days with bilirubin $<$ 2x ULN

If a subject fails to meet these retreatment criteria then the treatment cycle should be skipped.

The PI can be contacted at any time if further clarification is needed.

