3.1 Study Design and Duration

This study is a Phase 1/1b, open-label, single institution, dose escalation and dose expansion study to evaluate the efficacy, safety, and tolerability of APX005M in combination with nivolumab and cabiralizumab in patients with advanced melanoma, NSCLC, and RCC.

Nivolumab is a fully human monoclonal antibody directed against PD-1. Cabiralizumab is a humanized monoclonal antibody directed against CSF1R. APX005M is a humanized IgG1 agonistic monoclonal antibody that binds CD40.

Patients will be sequentially enrolled in the phase 1 dose escalation portion in 6 cohorts using a standard 3 + 3 design to determine safety, characterize the adverse events, and establish the MTD of APX005M in combination with cabiralizumab and nivolumab. A minimum of 48 hours observation will be required after each patient is enrolled in cohorts 1-6, before a subsequent patient can be enrolled. Approximately 3 patients will be enrolled into each cohort. Cohorts 1, 3, and 5 will include cabiralizumab at the fixed RP2D of 4 mg/kg and dose escalation of APX005M. Cohorts 2, 4, and 6 will include nivolumab at 240 mg, cabiralizumab at 4 mg/kg, and dose escalation of APX005M.

All study drugs will be given on Day 1 of each 14-day treatment cycle. Pre-medications will be given before nivolumab. Nivolumab will be administered as an IV infusion over 30 minutes first followed by a 30-minute break and then cabiralizumab will be administered as an IV infusion over 30 minutes. After another 30-minute break, APX005M will be administered as an IV infusion over 60 minutes. Patients must remain near the vicinity of a hospital with rapid access to an intensive care unit setting during the initial 48 hour period after treatment for the first two treatment cycles.

Dose escalation will be based on the number of DLTs experienced during the DLT evaluation interval as determined by the PI and Industry Collaborators (see Section 3.1.2.1.1 for DLT criteria). The DLT evaluation interval begins on the first day of treatment and continues for 28 days.

The phase 1b portion will enroll patients in three cohorts (advanced melanoma, NSCLC, and RCC) to study the RP2D of APX005M in combination with nivolumab and cabiralizumab.

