4.12 Infusion Delays and Missed Doses with Nivolumab, Cabiralizumab and APX005M

In case an infusion cannot be administered at a scheduled visit, it must be administered as soon as possible. If the delay is more than two days, the infusion at the originally scheduled visit will be considered a missed dose and the procedures at the next visit should be performed. There must be at least 12 days between study drug administration.

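### For drug-related AST/ALT >5 to ≤12x ULN lasting more than 7 days with bilirubin <2x ULN, Section 4.7 skips the cycle but Table 5 continues all three drugs; the text favours skipping without expressly ranking the two

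*Combined protocol and SAP*

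**What the plan says.** Section 4.7 sets a condition for every new cycle: "A new treatment cycle should be initiated only if all toxicities are" Grade 1 or lower, apart from listed exceptions. The AST/ALT exception has three parts: no more than 12x ULN, for no more than 7 days, with bilirubin below 2x ULN. If the condition is not met, "If a subject fails to meet these retreatment criteria then the treatment cycle should be skipped".

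Table 5 in Section 4.9 has a row for Grade 3 AST/ALT above 5x ULN whose condition ends "12x ULN) and bilirubin <2x ULN". Its entries are Continue for APX005M, cabiralizumab and nivolumab, with no duration. The next row holds all three drugs for values above 12x ULN "for >14 days and not decreasing on steroids and bilirubin <2x ULN".

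Two other texts bear on which rule applies. Section 4.6 says drug-related laboratory abnormalities need no delay "unless clinically indicated or specified in the protocol or abnormal laboratory management guidelines", and then refers to Sections 4.8 and 4.9. Section 4.9 speaks of a "temporary treatment hold (until re-treatment criteria are met".

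**The concern.** Two sections give instructions for the same laboratory finding, and only one of them has a time limit. Once the elevation has lasted more than 7 days, a clinician following Section 4.7 withholds the cycle and a clinician following Table 5 gives all three drugs. Either action departs from the other section.

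This is a safety decision. For the same course, Section 4.8 suggests corticosteroids after more than 7 days if the event is judged related to treatment. In Phase 1, within the first 28 days, it is a DLT under item 5c of Section 3.1.2.1.1 unless clearly due to another cause. Full dosing of a patient in that state should follow from a deliberate rule, not from which page was consulted.

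**Working it through.** No formula in the plan is at issue. The check sets the texts side by side and then asks whether the state can arise in ordinary practice.

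**1. The two rules, for AST/ALT >5 to ≤12x ULN with bilirubin <2x ULN**

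| Duration | Section 4.7 | Table 5 row | Agree? |
|---|---|---|---|
| ≤7 days | Exception applies; cycle may start | Continue all three | Yes |
| >7 days | Exception lost, toxicity is Grade 3; skip | Continue all three | No |

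**2. Same decision?** Yes. Section 3.1: "All study drugs will be given on Day 1 of each 14-day treatment cycle". Continue and skip therefore concern the same Day 1 dose.

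**3. Does another text settle it?**
- Section 4.6 accepts a delay that is specified in the protocol. Section 4.7 specifies one and a Continue entry does not, which favours skipping. But 4.6 then sends the reader to 4.8 and 4.9, where the row says Continue.
- Section 4.9 uses the re-treatment criteria to end a hold. This row never starts one.
- Section 4.8 covers supportive care and says it does not replace dose delays or modifications.
- Section 4.11 refers to Table 5 for discontinuation, not for skipping a cycle.

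**4. Can scheduled laboratory tests reach this state?** Section 4.12: "There must be at least 12 days between study drug administration". Sections 5.2.1 and 5.2.2 allow pre-dose tests up to 72 hours (3 days) before dosing. The shortest interval between consecutive pre-dose tests is 12 − 3 = 9 days, which exceeds 7. With the 24-hour window in note a of Appendix A (Phase 1), it is 12 − 1 = 11 days. An elevation present at one pre-dose test and still unresolved at the next has therefore passed the limit. Two high values do not by themselves prove continuous elevation: Section 1.4.3 says liver abnormalities after APX005M tend to resolve within 7 days, so two separate rises are possible. The repeat testing in note h of Appendices A and B can establish duration directly.

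**5. How common?** Section 1.4.1 reports Grade 3 or higher AST events in the earlier cabiralizumab study: 10/34 = 29% in Phase 1a and 14/195 = 7% in Phase 1b. These are event counts, without APX005M, not capped at 12x ULN and without duration. They show that the grade is familiar, not how often the conflict would occur.

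**6. The same pattern for CK.** At CK >15 to ≤20x ULN without evidence of myocarditis or myositis, Table 5 continues APX005M and nivolumab and holds cabiralizumab. Section 4.7 allows a new cycle only with CK up to 15x ULN.

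**The case against.** The best defence is that the protocol already answers the question. Section 4.6 asks only whether a delay is specified somewhere, and Section 4.7 specifies one. Section 4.7 is a necessary condition, while Section 4.9 calls its entries recommended modifications. Continue in a table about holding and discontinuing can simply mean that this row triggers no hold. Section 4.7, the steroid guidance in 4.8 and DLT item 5c all turn at about 7 days, so the intent looks recoverable. The trial has one site, and Sections 4.6 and 4.7 both point to the PI for questions.

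Most of that stands. A reader might infer that the protocol gives no guidance at all; the documents do not support that, and skipping is the better reading. What remains is that no sentence says so. The neighbouring row states a duration, so its absence here can look deliberate. If Section 4.7 governs every cycle, values above 12x ULN are already skipped at any duration, which leaves that 14-day Hold row with little to do. The title of 4.7, about resuming treatment, could also suggest that it applies only after a hold, although its operative sentence covers any new cycle. Access to the PI lowers the practical risk but does not state the rule.

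A reader might also infer that every such patient must receive steroids or is automatically a DLT. Section 4.8 offers suggested measures for events judged related, and the DLT definition excludes events clearly due to another cause.

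**Conclusion.** The inconsistency is real and narrow: one Table 5 row lacks the 7-day limit that Section 4.7 imposes, and the cross-references favour 4.7 without expressly ranking it above the table. It affects dosing conduct in both phases. No rate can be attached, because persistence beyond 7 days is not reported. The conclusion assumes that the elevation is drug-related and that the printed row is complete.

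It would be tempting to say that the escalation decisions or the Phase 1b efficacy test are compromised. They are not. The Table 3 DLT count includes such a patient, and the Simon figures do not depend on this rule. One minor loose end is in Section 3.1.2.1: read literally, it limits the MTD/RP2D calculation to patients with at least 2 doses, so a patient with a DLT whose second cycle was skipped would fall out of it. Replacement is only for reasons other than drug-related AEs, so that patient is not replaced.

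**What to change.** Change the Table 5 row to: continue if ≤7 days; hold if >7 days until the Section 4.7 criteria are met. Add a sentence that, for AST/ALT, the Section 4.7 criteria govern the start of each cycle. If the investigators intend to dose through these elevations, delete the 7-day limit from Section 4.7 instead. In the same edit, decide whether APX005M and nivolumab may be given at CK >15 to ≤20x ULN, and make Section 4.7 and Table 5 agree. As a minor clarification, state in Section 3.1.2.1 that a patient with a DLT in the first 28 days counts in the MTD/RP2D calculation even after one dose.

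The edit is wording only. The stricter option has a clinical cost: once past 7 days, dosing waits for Grade 1 or lower, so some doses are skipped. Treatment may end under the 12-week delay limit in Section 4.11, for elevations that Section 1.4 regards as a pharmacodynamic marker and not a safety signal. That trade-off is for the investigators to decide.
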